- Refer to Table 8 for detail schedule of sampling during inpatient at research center. There will be an extra PK sampling for subjects with premature withdrawal; for subjects having conditional follow-up visit for safety, no PK sampling is required.
- Physical examination includes assessments of the general appearance, skin and mucosa, superficial lymph nodes, head and neck, chest, abdomen, musculoskeletal, and neurological systems.
- Vital signs including blood pressure (systolic and diastolic pressures), pulse rate, body temperature, and respiration (frequency per minute) will be measured and recorded. Blood pressure and pulse rate will be recorded in a sitting position after the subject has rested comfortably for at least 5 minutes(The blood pressure normal range is considered ≥ 90 mmHg and ≤ 139 mmHg for SBP; ≥ 60 mmHg and ≤ 90 mmHg for DBP). At Day 1 and Day 8: Vital signs will be repeated prior to dosing and at 4 hours postdose. Vital signs will also be assessed at Day 10.

- h. Electrocardiogram (12-lead ECG, including QTc evaluation) will be performed 4 hours postdose at Day 1 and Day 8. Electrocardiogram will also be performed at Day 10 before discharge from research unit.
- Adverse events will be collected starting from Day -1, the AEs since the date of first signature of informed consent will be recorded. The following visits will record any AEs since the last visit.
- Subjects will be discharged on Day 10, after final sample collection and safety examinations are completed (final examination).
- k. If subject has AE during trial and ongoing at discharge, the subject has to come back for the conditional follow-up visit.

2 Sponsor, Investigators, and Trial Administrative Structure

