7.1.4 Washout Period

The 2 administrations of IMP are separated by a Washout of 7 days (inpatient). Washout begins postdose on Day 1 and continues for approximately 7 days.

7.1.5 Day 7

Subjects will refrain from all food and drinks except water from the evening after dinner of Day 7. They will have fasted for at least 10 hours at the time of drug administration (fasting group) or standard breakfast (fed group) next morning.

Trial eligibility assessments will include: physical examination and concomitant medications (Table 1).

If the subject is determined to be ineligible for any of the above assessments, the subject will be dismissed from the CRU and will not continue with the trial.

Any AEs will be collected and recorded on the eCRF.

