7.4.1.2 Methods of Recording and Assessing Adverse Events

At each trial visit, the subject will be queried on changes in his condition. During the reporting period of the trial any unfavorable changes in the subject's condition will be recorded as AEs, whether reported by the subject or observed by the Investigator.

All AEs must be documented in the appropriate section of the eCRF. Complete, accurate and consistent data on all AEs experienced for the duration of the reporting period (defined below) will be reported on an ongoing basis. Among these AEs, all serious AEs and nonserious ADRs must be additionally documented and reported using an SAE Report Form as described in Section 7.4.1.4.

The following aspects must be recorded for each AE in the eCRF:

- 1. Description of the AE in medical terms, not as reported by the subject
- 2. Date/time of onset (only in relation to administration of IMP: before, during, or after)
- 3. Severity Grade (Section 7.4.1.1), assessed by the Investigator according to the Qualitative Toxicity Scale
- 4. Causal relationship to the IMP applied per protocol, assessed by the Investigator
- 5. Action taken with regard to trial treatments
- 6. Concomitant medication
- 7. Outcome
- 8. Seriousness (appropriate criteria documented).

It is important that each AE report include a description of the event, its duration (onset and resolution dates (and times when it is important to assess the time of AE onset relative to the recorded treatment administration time), its severity, its causal relationship with the trial treatment,

any other potential causal factors, any treatment given or other action taken, and its outcome. In addition, serious cases should be identified and the appropriate seriousness criteria documented.

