Any adverse event (AE) with incomplete start/time and or end dates will be handled as described below for the classification as treatment-emergent, assignment to treatment periods, and calculation of duration.

- AE with unknown start time but known start date, will be imputed with a time of 00:00 hours, unless the start date corresponds to any given dosing date, in which case time of dosing will be used instead. However, if this results in a start time after end time of the AE, then the start time will be imputed to 00:00 hours instead.
- Any AE with completely unknown start date will be imputed with date and time of the first IMP administration, unless the end date (imputed if needed) is known and prior to first IMP administration. In the latter case, the start date will be missing.
- AE with partially missing start date but in the same year (when day and month are missing) or in the same month and year (if the day is missing) as first IMP administration then the start date will be replaced by the minimum between first IMP administration and AE resolution date. In all other cases the missing onset day or onset month will be replaced by 01.
- Adverse event with completely unknown end date will be imputed with the date of study completion (or in case of withdrawal, date of discontinuation).

Partially known end dates will be treated as follows:

- If only the day is missing, the last day of the month will be imputed or the date of study completion/discontinuation if earlier.
- If day and month are both missing, then the end date of 31 December will be imputed or the date of study completion/discontinuation if earlier.

Assignment to the different treatment periods will be performed after the imputations have been performed. An AE will be assigned to a specific treatment period if it occurs on or after the IMP administration scheduled for that period and before the IMP administration in the next period (or study completion for the last period).

Trial day:

Trial day will be calculated from the reference start date, and will be used to show start/end day of assessments and events. Reference start date is defined as the day of the first IMP administration in period 1. Trial Day 1 is the day of first IMP administration in period 1. The day before is defined as Trial Day -1 (no Trial Day 0 is defined). Trial day will be calculated accordingly:

- If the date of the event is on or after the reference start date then:

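### The AE start-date imputation in SAP Section 11 takes no account of the second dose, so most Period 2 events with an incomplete onset date are credited to the Period 1 product

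*SAP*

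**What the plan says.** SAP Section 11, under the handling of discontinued subjects and missing data, sets out how incomplete AE dates are completed. It says the results serve to classify treatment emergence, assign periods and calculate duration. Three rules matter here:

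- Onset day missing in the month and year of the first dose, or day and month missing in the same year: "then the start date will be replaced by the minimum between first IMP administration and AE resolution date".
- Start date wholly unknown: "Any AE with completely unknown start date will be imputed with date and time of the first IMP administration", unless the event is known to have ended before that dose.
- Other partial dates: "In all other cases the missing onset day or onset month will be replaced by 01".

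The order of steps is explicit: "Assignment to the different treatment periods will be performed after the imputations have been performed". An event belongs to a period if it occurs "on or after the IMP administration scheduled for that period and before the IMP administration in the next period".

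SAP Section 17.1.1 then tabulates TEAEs by treatment within each food group, including by severity and relationship. On collection, Protocol Table 1 schedules AE recording on each of Days 7, 8, 9 and 10, and its footnote on AE recording adds: "The following visits will record any AEs since the last visit".

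**The concern.** In a parallel-group trial, moving an incomplete onset date to the first dose is a cautious choice, because the only question is whether the event came before or after treatment. In this crossover the imputed date also decides which product the event is counted under. The doses are given on Day 1 and Day 8, usually in the same calendar month, so a month-and-year date often cannot separate the periods. The rule settles that ambiguity in favour of Period 1 every time.

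The rest of the SAP is aware of periods. The rule for a missing start time refers to any dosing date, and the TEAE definition in Section 17.1 refers to each period. The start-date rule is the exception.

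At stake is the by-treatment description of safety and tolerability, a secondary objective. Because a subject is counted once per treatment for the same AE, a moved event can also merge with a genuine Period 1 event. The subject then drops out of the Period 2 product's count for that term.

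**Working it through.** The plan gives no figure to reproduce, so the check applies the Section 11 rules to dates.

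**Inputs.** Doses on Day 1 and Day 8 (Protocol Section 6.3). True onset on Day 8, 9 or 10, after the second dose. Period 1 runs from the Day 1 dose to before the Day 8 dose (SAP Section 11).

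**Assumption.** Day 1 is equally likely on any date from 20 November 2017 (date of protocol version 2.0) to 20 June 2018 (so that Day 10 still falls in the planned second quarter). That is 213 dates × 3 onset days = 639 combinations. The work is at day level; an imputed 01 that equals the Day 8 dosing date counts as Period 2.

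**First-dose rule.** Imputed start = min(first dose, resolution date). A Period 2 event cannot resolve before Day 8, so the minimum is always the first dose and the event is always placed in Period 1. Example: Day 1 = 8 January 2018, Day 8 = 15 January, true onset 16 January recorded only as January 2018. The imputed start is 8 January, in Period 1.

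**01 rule, at one month boundary.** Let Day 1 fall j days before the first of the next month. The three onset days lie 7, 8 and 9 days after Day 1.

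- j = 1 to 6: all three onsets fall in the next month, and the 01 precedes Day 8. 6 × 3 = 18 combinations go to Period 1.
- j = 7, 8, 9: 3, 2 and 1 onsets fall in the next month, and the 01 is on or after Day 8. 3 + 2 + 1 = 6 combinations stay in Period 2.

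The assumed dates cross seven month boundaries: 7 × 18 = 126 to Period 1 and 7 × 6 = 42 to Period 2, together 168. The remaining 639 − 168 = 471 are same-month cases.

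Examples: Day 1 = 29 January with onset 6 February is imputed to 1 February, before the 5 February dose, so Period 1. Day 1 = 25 January with onset 2 February is also imputed to 1 February, which is the dosing date, so Period 2.

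**Results for true Period 2 events.**

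| Missing part of start date | First-dose rule, to Period 1 | 01 rule, to Period 1 | 01 rule, stays in Period 2 | Share moved |
|---|---|---|---|---|
| Day | 471 | 126 | 42 | 597/639 = 93.4% |
| Day and month (one year boundary) | 615 | 18 | 6 | 633/639 = 99.1% |
| Whole date | 639 | – | – | 100% |

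If Day 1 could fall from 1 October 2017, the day-missing share is (597 + 144)/789 = 93.9%. The same calculation for true Period 1 onsets (Days 1 to 7) leaves all of them in Period 1, so the error runs one way.

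These are shares of events that trigger a rule. They are not shares of all AEs.

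**The case against.** The strongest reply is that the rules should seldom be triggered. Subjects are inpatients from Day -1 to Day 10, the protocol asks for onset and resolution dates, and analysis waits until queries are resolved. Section 11 also has imputed information flagged in listings, so a moved event could be traced. Safety is descriptive, the bioequivalence decision is untouched, and an event after dosing remains a TEAE either way. All of this stands and keeps the point small. None of it makes the treatment column of the TEAE table right for an event that is moved.

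Four stronger readings are tempting and are not supported:

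- *Every Period 2 event with a missing onset day is misassigned.* True of the first-dose rules only. Under the 01 rule, 42 of 168 cross-month combinations stay in Period 2.
- *The recording visit is already on the AE record.* Protocol Table 1 says when AEs are collected, but the list of AE items in Protocol Section 7.4.1.2 does not include the visit. It does include "Date/time of onset (only in relation to administration of IMP: before, during, or after".
- *AE durations will be shown inflated.* Section 11 names duration as a use of the imputation and says imputed values appear in listings. Its trial-day paragraph says that partial dates stay partial and the corresponding durations are presented as missing. The SAP conflicts with itself, so no particular displayed duration can be asserted.
- *The rule favours one product.* With 13/13 and 9/9 allocation to sequences, each product is the Period 1 product for half of each group. The tendency is to blur a difference between products.

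**Conclusion.** The point holds as a minor error in a stated rule. For a true Period 2 event, the first-dose rules give the wrong period with certainty. The 01 rule does so in 126 of 168 cross-month combinations (75%). The 93.4% overall share rests on evenly spread Day 1 dates and hardly changes with the start of that range; the certainty under the first-dose rules rests on no such assumption.

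The number of affected events cannot be estimated from the documents and is probably very small. With 26 and 18 subjects, though, a single moved event could be visible in a table. The consequence is confined to period and treatment attribution in the AE outputs. How imputed dates and durations are displayed is a separate inconsistency within Section 11 that should be settled at the same time.

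**What to change.** Amend SAP Section 11 so that, for a partial or unknown AE start date, the imputed start is no earlier than the Period 2 dosing date and time when available information places onset after the Day 8 dose. That information would be:

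- a visit or entry date of first recording on Day 9 or later; or
- for an event first recorded on Day 8, the before/during/after item of Protocol Section 7.4.1.2, read against the Day 8 dose.

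Where neither source settles the period, keep the present rule and flag the event as period-uncertain in the listing. Apply the same lower bound to the 01 rule.

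In the same edit, reconcile the Section 11 statements on whether imputed dates and durations are shown and flagged or presented as missing.

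The cost is a few lines of SAP text and a small programming change. The data team must confirm that the visit or entry date of first recording is retained with the AE record; no new assessment of subjects is needed.

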12.1 Disposition of Subjects and Discontinuations

All subjects who provide informed consent will be accounted into this study. Subject disposition and withdrawals will be presented for the Screening Population.

The following summaries will be produced by treatment sequence and overall, for each food condition group:

- Total number of subjects screened (i.e. subjects who gave informed consent)
- Numbers of randomized subjects
- Number of subjects treated in each period
- Number of subjects who complete the trial
- Number of subjects who discontinued the study treatment after the first administration, grouped by the main reason
- Number of subjects who terminated the study prematurely, grouped by the main reason
- Number of subjects included in Safety Population
- Number of subjects included in PK Population

Corresponding individual listings will be prepared (sorted by group, treatment sequence and subject).

Additionally, a listing of the screening failures will be produced with the reason of non-inclusion in the treatment phase.

Listings with visit dates will also be carried out by group, treatment sequence and subject.

12.2 Protocol Deviations

12.2.1 Important Protocol Deviations

Important protocol deviations will be based on the Clinical Trial Management System (CTMS) data and determined by medical review process. All important protocol deviations will be included in SDTM datasets, if identified through medical review. The Analysis Data Model (ADaM) datasets will be derived from SDTM and include all important protocol deviations.

A data review meeting will be held to discuss and update the definition of important protocol deviations so as to determine the evaluability of the subjects prior to database lock.

The following outputs will be provided by treatment sequence and overall, for each food condition group:

- Summary of important protocol deviations relating to inclusion/exclusion criteria
- Summary of other important protocol deviations post inclusion criteria

All important protocol deviations will be listed. A listing presenting protocol deviations relating to inclusion/exclusion criteria and a listing presenting other deviations will be produced.

13 Demographics and Other Baseline Characteristics

Unless otherwise specified, demographic data and other baseline characteristics will be presented for the Safety Population.

Summaries of the key demographics overall and by treatment sequence for each group are to be provided. Continuous variables will be summarized using the descriptive statistics. Qualitative variables will be summarized by counts and percentages. No statistical testing will be carried out for demographic or other baseline characteristics.

13.1 Demographics

Demographic characteristics will be summarized using the following information from the Screening/Baseline Visit eCRF pages.

Demographic characteristics

- Age (years): summary statistics
- Sex: Male, Female
- Race: Chinese, Non-Chinese
- Weight (kg): summary statistics
- Height (cm): summary statistics
- BMI (kg/m²): summary statistics

Specifications for computation:

- Age (years):
- (date of given informed consent - date of birth + 1) / 365.25

13.2 Medical History

The medical history will be summarized from the “Medical History” eCRF page, using MedDRA, Version 20.1 or higher version, preferred term (PT) as event category and MedDRA system organ class (SOC) body term as Body System category.

Medical history will be displayed in terms of frequency tables: ordered by primary SOC and PT in alphabetical order.

13.3 Other Baseline Characteristics

The following baseline characteristics will be reported overall and by treatment sequence for each group:

- Nicotine and Alcohol Consumption
- Urine Testing of drugs of abuse
- Breath test of alcohol
- Serology: HAV antibody, HBsAg, HCV antibody, HIV antibody, TP antibody

Baseline characteristics with respect to vital signs, ECG recordings and laboratory tests will be part of Section 17 (Safety Evaluation).

Results of chest x-ray and serum pregnancy test (for women of childbearing potential) will be presented only in the listings.

14 Previous or Concomitant Medications/Procedures

Previous and concomitant medication/ procedure will be tabulated for Safety Population. All medications and procedures will be presented in the listings.

Medications will be coded using World Health Organization Drug Dictionary Enhanced (WHO-DDE) Version 01Sep2017 or higher version. Procedures will be coded using MedDRA Version 20.1 or higher version.

Previous medications are medications started and ended before first IMP administration.

Concomitant medications/ procedures are medications/ procedures, other than trial medications/ procedures, which are taken by subjects any time on-trial (include medications/ procedures which started before the first IMP administration and were ongoing after first IMP administration, or started on or after the first IMP administration day).

Previous and concomitant medications will be summarized overall for both groups as well as overall and by treatment sequence for each group, and by PT and ATC 2nd level, respectively. The listing of previous and concomitant medications/procedures will be generated.

Concomitant procedures will be summarized overall for both groups as well as overall and by treatment sequence for each group, and by reason for procedure and PT, respectively. The listing of previous and concomitant procedures will be generated.

15 Treatment Compliance and Exposure

Safety Population will be used to list the IMP administration. IMP administration will be listed by group, treatment sequence and subject with treatment, date and time of administration.

Missing or partial dates or time for IMP administration will not be imputed.

16 Endpoint Evaluation

16.1 Primary Endpoint Analyses

The primary endpoints are the following PK parameters calculated from metformin plasma concentrations:

AUC_{0→t} of metformin

C_{max} of metformin

The null and alternative hypotheses are the following:

H_0 : for AUC_{0-t} $\mu_T / \mu_C \leq 0.8$ or $\mu_T / \mu_C \geq 1.25$
for C_{max} $\mu_T / \mu_C \leq 0.8$ or $\mu_T / \mu_C \geq 1.25$, for at least 1 primary endpoint

H_1 : for AUC_{0-t} $0.8 < \mu_T / \mu_C < 1.25$
for C_{max} $0.8 < \mu_T / \mu_C < 1.25$, for both primary endpoints and for both fasting and fed groups

where μ_T and μ_C are the means of primary endpoints following test IMP and reference IMP (Treatment A and Treatment B), respectively.

The analysis of primary endpoints will be based on PK Population ([Section Error! Reference source not found.](#))

The primary endpoints, C_{max} and AUC_{0→t} in fasting and fed group, will be log-transformed and a mixed-effects model will be applied. The model will include fixed effects for sequence, treatment and period and a random effect of subject nested within sequence. Treatment differences on the log scale will be estimated for the parameters together with their 90% CIs. The least squares means together with their 95% CIs by treatment will also be estimated. Point estimates and CIs will be back-transformed to the original scale for presentation, i.e., ratios of geometric means and corresponding 90% CIs for Treatment A/Treatment B, and geometric means and corresponding 95% CIs by treatment, respectively. Intra-subject CV estimated from the model will also be presented. Bioequivalence will be assessed separately in the fed and in the fasted group, and the trial will be considered successful only if BE is established for both primary parameters in both groups. The BE will be considered established if the 90% CIs for the ratios of geometric means between the investigational product and the comparator fall within 80.00% to 125.00% for all these comparisons.

The following example code could be used:

```
proc mixed data=pkparam;  
  by food param;  
  class sequence period trt subjid;  
  model lnest = sequence period trt /ddfm=kr;
```

```
random subjid(sequence);  
estimate 'A vs B' trt 1 -1 /alpha=0.1 cl;  
lsmeans trt /alpha=0.05 cl;
```

run;

All primary PK endpoints will be descriptively summarized as described in Section **Error! eference source not found.** Graphs of individual values and geometric mean will be presented for primary PK parameters versus treatment and food condition. Boxplots will also be created for primary PK parameters versus treatment for the fed and the fasted conditions.

16.2 Secondary Endpoint Analyses

All secondary PK endpoints will be descriptively summarized as described in Section 11. The secondary PK endpoints are the following parameters in plasma for metformin:

t_{\max} , $t_{1/2}$, λ_Z , $AUC_{0 \rightarrow \infty}$, $AUC_{\text{extra}\%}$, CL/f , $V_{z/f}$.

For t_{\max} , the Hodges-Lehmann estimates for the treatment differences and corresponding 90% CIs according to the Tukey method will be calculated.

The mixed-effects model for treatment comparison as described for the primary endpoints will also be applied to $AUC_{0 \rightarrow \infty}$. The ratios of geometric means and corresponding 90% CIs for Treatment A/Treatment B will be estimated separately for fed and fasted treatments. Graphs of individual $AUC_{0 \rightarrow \infty}$ values and geometric mean will be presented by treatment and food condition.

